**Aim 2. Examine maintenance of treatment effects on primary outcomes:**

***Hypothesis 2: Treatment effects will be maintained at follow up in both groups.***

Differential treatment effect of STEP-Home over PCGT T4 will be maintained at T5

Statistical Methods: Mixed models, as described under Hypothesis 1B. We hypothesize that there will not be a significant interaction between group and time-point but the main effect of group will remain significant. Since subjects may initiate behavioral therapy post-intervention, we will conduct a secondary analysis to evaluate the impact of additional psychotherapy on the treatment effects. We will stratify by group and post-intervention therapy status (therapy/no therapy) and examine paired t-tests within each of the 4 strata.

**Exploratory Aim 1. Explore treatment effects of STEP-Home on measures of mental health, functional and vocational status and cognitive secondary outcomes targeted indirectly in the workshop.**

Statistical Methods: Paired t-tests and mixed models, as described in Primary Aims 1 and 2.

**Exploratory Aim 2. Acquisition of core skills (problem solving, emotional regulation, attention training) will mediate the effect of treatment on the primary outcomes post-intervention and follow up.**

Veterans demonstrating greater acquisition of core skills will evidence greater improvement in reintegration, readjustment, and anger post-intervention (T4) and at follow up (T5).

Statistical Methods: Exploratory mediation analyses will evaluate the potential causal pathway between treatment allocation and each primary outcome, with the core skills as mediators, using the SAS *mediation*

macro developed by Valeri and VanderWeele [88]. We will run separate mediation analyses for each primary outcome and with each core skill (PS, ER, AT) as the mediator. We will evaluate acquisition of skills at two separate times during intervention (T2 and T3) as mediating the effect of treatment on post-intervention (T4). We will also examine skill acquisition at post-intervention (T4) as mediating the effect of treatment at follow up (T5). The mediation analysis will fit two models: (1) linear regression with the primary outcome as the dependent variable, group as the independent variable, and the mediator as a covariate and (2) linear regression with the mediator as the dependent variable and group as the independent variable. Both models adjust for any identified group-outcome and mediator-outcome confounders. The direct and indirect (mediating) effects are calculated from the beta coefficients of these two models and the 95% confidence intervals calculated using bootstrap (1000 replications). We will conduct a secondary analysis to evaluate the impact of any behavioral therapy initiated post-intervention for the post-intervention mediation analysis (i.e. core skills mediating effect T4 - T5), stratifying by post-intervention therapy status (therapy/no therapy).

**Power Analysis.** Power calculations are made for the full study, including Phase 2 recruitment at site 2 (Houston). Power calculations were conducted on the primary aims (Aims 1 and 2) to observe an effect of Cohen's  $d=0.44$  or larger at one-tailed  $p<.05$  and  $\geq 80\%$  power. We selected a one-tailed p-value because all primary hypotheses were stated *a priori* as one-sided. We anticipated a small to medium effect size based on the Cohen's  $d=0.44$  observed in the subset of our SPiRE feasibility study ( $n=35$ ) who reported at least some difficulty on M2CQ, WHODAS, or Impulsive Aggression Scale (IAS). While we did not specifically collect pilot data on the PDRI or STAXI-2, we assume the effect size will be at least as strong as  $d=0.44$  observed on the proxy measures (WHODAS and IAS) since the PDRI and STAXI-2 are more sensitive and specific to post-9/11 Veterans. We further applied a conservative attrition rate of 20%, based on the attrition observed in our SPiRE feasibility study [1] and in Mt. Sinai's STEP RCT [2]. The univariate paired t-tests evaluating the improvement (Hypothesis 1A) and post-intervention maintenance (Hypothesis 2) of primary outcomes scores within the intervention groups required a total sample size of 83 after accounting for attrition. For Hypotheses 1B, the sample size was further adjusted to account for the clustering of subjects within the randomization cohort by applying an inflation of variance factor [71,89]. We used an interclass correlation of  $r=0.04$  as observed in a similarly designed group therapy RCT [65]. For the univariate post-intervention and change score analyses, we would need a total sample size of 208 after accounting for clustering and attrition. Thus, a total sample size of 208 is sufficient to power both primary aims.

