**Aim 1. Examine treatment effects of STEP-Home on primary outcomes relative to PCGT:**

***Hypothesis 1A. Participants randomized into the STEP-Home intervention will show improvement on reintegration, readjustment, and anger post-intervention (expressed by lower scores; less difficulty).***

Military to Civilian Questionnaire (M2CQ), Post-Deployment Readjustment Inventory (PDRI), and State-Trait Anger Expression Inventory (STAXI-2) scores post-intervention (T4)  $<$  baseline (T1)

Statistical Methods: Paired t-tests will evaluate the difference between pre- (T1) and post-scores (T4), with a separate analysis for each primary outcome.

***Hypothesis 1B. Participants randomized into STEP-Home will show greater improvement in primary outcomes as compared to PCGT.***

1B.1: Change scores baseline (T1) to post-intervention (T4) STEP-Home  $>$  PCGT

1B.2: Post-intervention (T4) primary outcome scores STEP-Home  $<$  PCGT

Statistical Methods: Mixed models (PROC MIXED in SAS) will evaluate pre-post differences, with a separate model for each primary outcome. The Satterwaite option will be used to account for the clustering of subjects within cohorts (identified in Section 6.2) and calculate degrees of freedom accounting for any missing data. Group (STEP-Home/PCGT) will be the between-subjects factor and time-point (T1/T4) will be the within-subjects factor. We hypothesize that there will be a significant interaction between group and time-point, with a larger improvement between pre- (T1) and post-scores (T4) in STEP-Home than PCGT. While we do not anticipate a significant interaction by cohort or site, we will evaluate the 4-way interaction and all 2-way and 3-way interactions for time-point, group, cohort, and site. The model will be rerun removing any non-significant interactions. Linear regression will be used to evaluate the difference in post-intervention (T4) by group. The final mixed and regression models for each outcome will adjust for any identified confounders.

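### Hypothesis 2 reads a lasting STEP-Home advantage from a non-significant interaction and an averaged group effect, with no between-arm test at T5

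*Combined protocol and SAP*

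**What the plan says.** Under Aim 2 of the Analytic Plan, Hypothesis 2 has a within-arm part (effects hold at follow-up in both groups) and a between-arm part: "Differential treatment effect of STEP-Home over PCGT T4 will be maintained at T5". The stated method is "Mixed models, as described under Hypothesis 1B", with the expected result "We hypothesize that there will not be a significant interaction between group and time-point but the main effect of group will remain significant".

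The model referred to is specified under Hypothesis 1B: "Group (STEP-Home/PCGT) will be the between-subjects factor and time-point (T1/T4) will be the within-subjects factor". The only group comparison there at a single time point is at T4: "Linear regression will be used to evaluate the difference in post-intervention (T4) by group".

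A secondary analysis deals with therapy begun after the intervention: "We will stratify by group and post-intervention therapy status (therapy/no therapy) and examine paired t-tests within each of the 4 strata".

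The Power Analysis paragraph sizes Hypothesis 2 on within-arm paired t-tests: "post-intervention maintenance (Hypothesis 2) of primary outcomes scores within the intervention groups required a total sample size of 83 after accounting for attrition". It then concludes: "Thus, a total sample size of 208 is sufficient to power both primary aims".

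**The concern.** - **Inference from a null result.** Failing to reject the group-by-time interaction may only mean that the test had little power. It is not evidence that the advantage lasted.
- **The main effect does not isolate T5.** In a model of T4 and T5, the group effect is the average of the two between-arm differences. A benefit at T4 can make it significant when little is left at T5.
- **The model is not defined.** Read literally, the cross-reference gives a T1/T4 model with no T5 data. If T1 is kept and T5 added, a lasting benefit would itself create the interaction that Hypothesis 1B expects to be significant, so the predicted null would contradict it.
- **Model reduction.** Hypothesis 1B also has the model refitted without its non-significant interactions. If that carries over to Aim 2, dropping group-by-time forces the T4 and T5 differences to be equal, and no separate T5 estimate remains.
- **Power.** The Hypothesis 2 figure is for within-arm tests. It does not show that 208 powers the between-arm part.
- **Secondary point.** The four-strata paired t-tests condition on therapy started after randomisation and do not compare the arms. They cannot show how later therapy affects the between-arm difference. Differential uptake is possible but not established.

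At stake is a primary-aim claim that the differential effect was maintained at T5 when about half of it is gone, or when the T5 difference is not itself significant. Aim 1 is not affected.

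**Working it through.** **Inputs from the plan.** d=0.44, one-sided 5%, 80% power, 20% attrition and ICC 0.04 (Power Analysis); therapy groups of 8 and equal arms (Study Design); 208 total (Power Analysis) and 240 as the updated enrolment target (Study Design).

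**Assumptions not in the plan.** A T4/T5 model, T4–T5 correlation r from 0.5 to 0.8, equal variances, a two-sided 5% interaction test, normal approximations, and a design effect on the interaction (DE_I) of 1 or 1.28.

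**1. The plan's own figures reproduce.** The design effect is 1+(8−1)×0.04 = 1.28. A one-sided two-sample t-test at d=0.44 with 80% power needs 65 per arm, and 2×65×1.28/0.80 = 208. A one-sided paired t-test needs 33.33 per group, and 2×33.33/0.80 = 83.3, the stated total of 83. So 208 belongs to the Hypothesis 1B comparison and 83 to within-arm tests.

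**2. Analysed numbers.** 208×0.80/2 = 83 per arm (the match with the plan's total of 83 is coincidence). 240×0.80/2 = 96 per arm.

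**3. Probability of the predicted pattern.** Let v = 2/n, which is 0.0241 at n=83.
- SE(interaction) = √[2(1−r)·v·DE_I]
- SE(average group effect) = √[(1+r)/2·v·1.28]

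Under equal variances the two estimates are independent, so P(pattern) = P(|z_int|<1.96) × P(z_main>1.645).

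Example with half the advantage lost (T4 0.44, T5 0.22), r=0.5, DE_I=1.28. SE(interaction) = 0.1756, so z = 0.22/0.1756 = 1.25 and P(not significant) = 0.760. SE(average) = 0.1521, so z = 0.33/0.1521 = 2.17 and P(significant) = 0.700. The product is 0.532.

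| 83 per arm | r=0.5 | 0.6 | 0.7 | 0.8 |
|---|---|---|---|---|
| Half lost, DE_I 1.28 | 53.2% | 48.1% | 41.4% | 31.1% |
| Half lost, DE_I 1 | 49.4% | 43.7% | 36.0% | 24.6% |
| All lost, DE_I 1.28 | 12.3% | 8.1% | 3.9% | 0.8% |
| All lost, DE_I 1 | 8.0% | 4.6% | 1.7% | 0.2% |

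At 96 per arm the half-lost range is 22.4% to 55.0%, so the larger enrolment does not remove the problem. By simulation (600,000 draws, half lost, 83 per arm), the T5 contrast is not itself significant in about 28% to 41% of the trials that show the pattern.

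**4. Smallest observed T5 difference that passes.** With an observed T4 difference of 0.44 SD this is the larger of 0.44−1.96·SE(interaction) and 2×1.645·SE(average)−0.44.
- r=0.5, DE_I 1.28: max(0.096, 0.060) = 0.096 SD.
- r=0.8, DE_I 1: max(0.248, 0.108) = 0.248 SD.

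That is 22% to 56% of the T4 difference. One-sided significance at T5 needs 1.645·SE(T5) = 0.281 to 0.289 SD.

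**5. A direct T5 contrast.** SE = √(v×1.28) = 0.1756 at 83 per arm.
- Full 0.44 kept: Φ(0.44/0.1756−1.645) = 80.5%. At 96 per arm it is 85.3%.
- Half kept: Φ(0.22/0.1756−1.645) = 34.7%.
- Nothing kept: 5%.

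**6. An illustrative 50% retention test.** Test T5−0.5×T4 > 0, one-sided 5%, with the advantage fully kept. At r=0.5 and DE_I 1.28, SE = √[v×1.28×(1.25−r)] = 0.1521 and power is Φ(0.22/0.1521−1.645) = 42%. Over r and DE_I the range is 42% to 63% at 83 per arm.

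**The case against.** The plan states an expected pattern, not a formal decision rule, so the pass rates describe a test it never spells out. That is literally true, but the plan gives no other between-arm inference for Hypothesis 2.

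The wording of the hypothesis points to T4 and T5, and the predicted pattern makes sense only in that model. This is fair, and it is the reading used in the calculation. The cross-reference still leads to a T1/T4 model.

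The figures rest on choices the plan does not make. A one-sided 5% interaction test, in keeping with its one-sided hypotheses, lowers the half-lost range at 83 per arm from 25%–53% to 17%–46%, and the all-lost range from 0%–12% to 0%–8%. The half-lost rate is still substantial.

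The two-part pattern gives some protection. For complete loss with r of 0.7 or more it passes in at most 4% of trials, below the 5% of a direct T5 test. For half loss at r=0.8 it passes in 25% to 31%, below the direct contrast's 35%. This stands: the T5 contrast alone does not identify maintenance better. The gain comes from claiming only what the contrast supports and from reporting intervals.

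The power point is a missing demonstration and not a shortfall, since 208 does give about 80% for a T5 contrast at d=0.44. The four-strata analysis is labelled secondary. Both points are accepted.

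**Conclusion.** The concern holds and should be fixed before the analysis. As written, the only between-arm inference for Primary Aim 2 can support a claim of maintenance after substantial loss. If half the advantage is gone by T5, the predicted pattern appears in 25% to 53% of trials with 208 enrolled and 22% to 55% with 240. These figures depend on the assumed T4–T5 correlation of 0.5 to 0.8, a two-sided interaction test, equal variances and the design effect applied to the interaction. The problem is partial loss; complete loss is seldom missed. The stated sample sizes of 208 and 83 are arithmetically sound, and the Aim 1 comparison is untouched.

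**What to change.** 1. Name the time points for Aim 2: one mixed model with T1, T4 and T5 that accounts for clustering. Keep group-by-time in it whatever its p-value.
2. Make the STEP-Home minus PCGT contrast at T5 (adjusted for T1, or as change from T1), with a confidence interval at the trial's alpha, the test of the between-arm part of Aim 2. Word a positive result as an advantage present at T5.
3. Report the T4-to-T5 change in the between-arm difference as an estimate with a confidence interval. Do not cite a non-significant interaction as evidence.
4. Use the word 'maintained' only against a prespecified retention margin, with its power stated.
5. Restate Aim 2 power for the T5 contrast: about 80% with 208 and 85% with 240 enrolled, if d=0.44 persists.
6. Label the four-strata paired t-tests as descriptive and report therapy uptake by arm.

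The cost is SAP wording and one ESTIMATE or CONTRAST statement. T5 assessments are already scheduled, and neither new data nor a change in enrolment is needed. The downside is a narrower claim: without a margin the trial can report only an advantage present at T5, and a 50% margin would be underpowered.

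### Hypothesis 2 claims maintenance in both arms, but its stated success pattern uses only between-arm contrasts and cannot see an equal loss in both; the power section names a different test

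*Combined protocol and SAP*

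**What the plan says.** Section 1(b), Hypotheses & Aims, and Aim 2 of the Analytic Plan both head Hypothesis 2 with a statement about each arm: "Treatment effects will be maintained at follow up in both groups". Aim 2 then restates it as a comparison between arms: "Differential treatment effect of STEP-Home over PCGT T4 will be maintained at T5".

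The Statistical Methods under Aim 2 refer back to the mixed models of Hypothesis 1B, do not list the time-points, and state the expected result: "We hypothesize that there will not be a significant interaction between group and time-point but the main effect of group will remain significant". The effect of time-point is not part of that result.

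Within-arm tests appear in two other places:

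- Aim 2 has a secondary analysis of psychotherapy started after the intervention: "We will stratify by group and post-intervention therapy status (therapy/no therapy) and examine paired t-tests within each of the 4 strata".
- The Power Analysis paragraph attributes Hypothesis 2 to univariate paired t-tests, and says that the "post-intervention maintenance (Hypothesis 2) of primary outcomes scores within the intervention groups required a total sample size of 83 after accounting for attrition". It does not say which two visits are paired.

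**The concern.** The headline claim concerns what happens inside each arm after treatment ends. The group main effect and the group by time-point interaction are both differences between arms. A change shared by both arms goes into the time-point effect, which the success pattern does not use. A result could therefore fit the pattern, and be reported as maintenance in STEP-Home and in PCGT, although PCGT has lost its whole gain and STEP-Home a good part of its own.

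Shifts shared by both arms are plausible here. The exclusion-criteria text allows and encourages all participants to start other treatment during follow-up, so both arms may move together in either direction.

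The power section does not settle the matter. It names a different test for the same hypothesis and leaves the visits open.

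**Working it through.** **1. The plan's own figures.** Inputs from the Power Analysis paragraph: d = 0.44, one-sided 0.05, 80% power, ICC 0.04, attrition 20%. Group size 8 is the goal in Section 4(b).

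- Between-arm: a two-sample t-test needs 65 per arm (power 80.2%). Design effect 1 + (8 - 1) x 0.04 = 1.28. Total 2 x 65 x 1.28 / 0.80 = 208. This reproduces the plan.
- Within-arm: a paired t-test with n = 33 has power 79.6%, and 2 x 33 / 0.80 = 82.5, or 83. With n = 34 (80.7%) the total is 85. The plan's 83 is reproduced to within rounding.

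The plan's 83 is a total over both arms. By coincidence, 208 x 0.80 / 2 also gives about 83 completers per arm, the number used below.

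**2. Equal loss (algebra only).** Write S4, S5, P4, P5 for the arm means (S = STEP-Home, P = PCGT). In a T4/T5 model:

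- group main effect = [(P4 - S4) + (P5 - S5)] / 2
- interaction = (P5 - S5) - (P4 - S4)

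Add the same loss c to every T5 score. P5 - S5 is unchanged, so both contrasts are unchanged. Their standard errors do not change either, because a constant adds no variance. The invariance also holds if T1 is in the model.

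**3. How often the pattern is met.** Assumptions not in the documents: unit SD at each visit, a T4/T5 model, T4-T5 correlation rho, a group ICC constant over time, and an interaction tested two-sided at 0.05. The group test is one-sided, as in the power section. With 83 completers per arm:

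- SE(group) = sqrt[((1 + rho)/2) x 2 x 1.28/83]
- SE(interaction) = sqrt[2(1 - rho) x 2/83], because a constant group effect cancels in the change
- P(met) = P(group significant) x P(interaction not significant)

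Example, rho = 0.7: SE(group) = 0.162 and SE(interaction) = 0.120.

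- Gains kept, or equal loss: 0.44/0.162 = 2.72, power 0.858; 0.858 x 0.95 = 0.815.
- Each arm back at its own baseline (difference 0.44 at T4, 0 at T5): the group contrast is 0.22, power 0.387. The interaction is 0.44/0.120 = 3.66, not significant with probability 0.045. Product 0.017.

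| rho | gains kept or equal loss | between-arm difference halved at T5 | each arm at own baseline |
|---|---|---|---|
| 0.5 | 0.849 | 0.494 | 0.080 |
| 0.6 | 0.832 | 0.437 | 0.046 |
| 0.7 | 0.815 | 0.360 | 0.017 |
| 0.8 | 0.798 | 0.246 | 0.002 |
| 0.9 | 0.782 | 0.069 | 0.000 |

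Simulation with 13 groups of 8 per arm gave 0.836, 0.805 and 0.787 at rho 0.5, 0.7 and 0.8. The rates were identical with no loss, with 0.30 SD lost in both arms and with 0.74 SD lost in both. With each arm at its own baseline the rates were 0.094, 0.024 and 0.002.

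For scale, assume a PCGT gain of 0.30 SD (the documents give none), so that STEP-Home gains 0.30 + 0.44 = 0.74 SD. An equal loss of 0.30 SD puts PCGT back at baseline and costs STEP-Home 0.30/0.74 = 41% of its gain.

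**4. Other readings of the inputs.** A two-sided group test gives 0.69-0.78 for rho 0.9 to 0.5. The updated target of 240 gives 0.825-0.882 if 192 complete, and 0.880-0.918 if 240 complete.

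**5. The paired t-test as a T4-T5 test.** With 83 per arm and clustering ignored, a true loss of 0.22 SD of change (half of 0.44) is non-significant in 37% of trials one-sided and 49% two-sided.

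**The case against.** **The sentence states an expectation, and its operational line is between-arm.** Both points are true, and the pattern suits the differential claim. The plan also promises means and SDs by arm at each time point, so a shared decline would show in the tables. But no criterion is then left in Aim 2 for the both-arms statement that heads the hypothesis.

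**The plan has a within-arm test.** A reader might infer that nothing in the plan looks within arms. The documents do not support that: the power section sizes paired t-tests for this purpose. For a loss of 0.30 SD they would be useful, with one-sided power per arm at n = 83 of 86% (rho 0.5) to 97% (rho 0.7), ignoring clustering. The accurate criticism is that Aim 2 and the power section disagree and the visits are not named. If T4 and T5 are meant, a non-significant result is not evidence of maintenance. The four-strata t-tests address added psychotherapy in subgroups formed after treatment.

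**Relapse would break the pattern.** A reader might infer that the pattern is blind to any relapse of the two arms together, or that the conclusion has nothing to do with durability. That goes too far. If each arm returns to its own baseline, the between-arm difference vanishes and the pattern is rarely met. If each loses half its gain, the rate roughly halves or falls further. Only an equal absolute loss passes unseen. An equal loss of 0.74 SD would put PCGT 0.44 SD below its own baseline, which nothing in the documents suggests.

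**The rate depends on the model.** This stands. If T1 is included, an effective treatment should itself produce a significant interaction, and simulations met the pattern in no more than about a fifth of trials even with all gains kept. The invariance needs no such assumption.

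**Conclusion.** The point holds in a limited form. The success pattern stated for Hypothesis 2 can support a claim about the STEP-Home advantage, but not a claim that each arm kept its gain. Equal absolute loss in both arms leaves the chance of meeting the pattern exactly unchanged; this is algebra.

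The level of that chance, about 78-85%, is conditional on 208 randomised, 20% attrition, ICC 0.04, a true difference of 0.44 SD, a T4/T5 model, a one-sided group test and a T4-T5 correlation of 0.5-0.9. It is close to the power for the between-arm difference and carries no separate weight. The pattern does respond to unequal loss, falling to about 0-9% when each arm returns to its own baseline (correlation 0.5-0.8).

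Separately, and without any assumption, Aim 2 and the power section name different tests for one primary hypothesis and should be reconciled.

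**What to change.** Use the mixed-model between-arm contrasts for the differential claim only, and list the time-points in the model. Make Aim 2 and the Power Analysis name the same within-arm analysis. For each arm and each primary outcome, report from the mixed model, with clustering, the T4-to-T5 change and the T1-to-T5 change, each with a 95% confidence interval.

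Base any statement about both arms on the two together. A T1-to-T5 improvement shows only that some gain remains. In simulation, STEP-Home after losing 41% of its gain would still show a significant T1-to-T5 improvement in 96-99.5% of trials. The T4-to-T5 interval shows how much loss is excluded. State that within-arm change is uncontrolled: entry requires reported difficulty, so regression to the mean is possible, and therapy during follow-up may contribute.

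The alternative is to remove the both-arms wording and limit Hypothesis 2 to the between-arm claim.

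The cost is wording and two contrasts per arm and outcome, on data already scheduled at T1, T4 and T5. The both-arms claim becomes harder to meet. With an assumed PCGT gain of 0.30 SD fully kept, the T1-to-T5 part alone is significant in about 75-88% of simulated trials (correlation 0.5-0.7).
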